4.1. Rationale for Study Population

Since AERD is virtually always an adult-onset disease, adults will comprise all of the study subjects. AERD affects both sexes and all races; no exclusions will be made based on sex or ethnicity.

4.2. Inclusion Criteria

Individuals who meet all of the following criteria are eligible for enrollment as study participants:

1. Subject must be able to understand and provide informed consent
2. Age between 18 and 70 years
3. History of AERD, defined as meeting the diagnostic triad with:
 - a. History of physician-diagnosed asthma **and**
 - b. History of physician-diagnosed nasal polyposis **and**
 - c. History of pathognomonic reactions to aspirin or other nonselective COX inhibitors.

To ensure all patients stringently meet this criteria and truly have AERD, we will require that patients either:

1. Have a history of at least two pathognomonic clinical reactions to aspirin or other nonselective COX inhibitors with features of lower (cough, chest tightness, wheezing, dyspnea) and/or upper (rhinorrhea, sneezing, nasal obstruction, conjunctival itching and discharge) airway involvement.
Or...
2. Have had a confirmatory physician-administered challenge with aspirin or another nonselective COX inhibitor that induced a pathognomonic respiratory reaction as above.

4. Stable asthma (post-bronchodilator FEV₁ of $\geq 70\%$, no glucocorticoid burst (increase $\geq 10\text{mg}$ per day or doubling daily dose, whichever is less) for at least 2 weeks prior to Visit 1, and no hospitalizations or ER visits for asthma for at least 6 months prior to Visit 1), and for those patients on daily oral steroids, they must require no more than a daily dose of 10mg prednisone or equivalent for their standard daily therapy to be considered for inclusion.
5. For females: Non-pregnant and practicing adequate birth control or abstinence
6. For males: practicing adequate birth control or abstinence
7. No current smoking (not more than one instance of smoking in the last 3 months)

4.3. Exclusion Criteria

Individuals who meet any of these criteria are not eligible for enrollment as study participants:

1. Inability or unwillingness of a participant to give written informed consent or comply with study protocol
2. Hypersensitivity to montelukast
3. Current use of zileuton (which blunts the peak levels of urinary LTE₄ during reactions)
4. Any history of bleeding diathesis or current use of anticoagulant/antiplatelet drugs
5. Any history of gastrointestinal bleeding
6. Current use of oral beta blockers, though ophthalmic formulations are acceptable

7. The use of an additional non-steroidal anti-inflammatory drugs (NSAIDs), except the aspirin dosing as detailed for the study
8. Use of any biologic therapy within the prior 4 months (120 days) of Visit 1.
9. History of cardiac rhythm disturbances.
10. Heart rate of <50 bpm at Screening Visit, or evidence of any type of heart block on ECG at Screening Visit.
11. Pregnant, nursing, or planning to become pregnant.
12. Past or current medical problems or findings from physical examination or laboratory testing that are not listed above, which, in the opinion of the investigator, may pose additional risks from participation in the study, may interfere with the participant's ability to comply with study requirements or that may impact the quality or interpretation of the data obtained from the study.
13. Evidence of liver failure (AST or ALT levels >3x normal at Screening)
14. Evidence of kidney failure (creatinine levels >1.5mg/dl in women and >1.7mg/dl in men)

5. Known and Potential Risks and Benefits to Participants

5.1. Risks of Investigational Product or Intervention as cited in Investigator Brochure or Package Insert

Risks of Ifetroban:

The pharmacodynamics of ifetroban were studied in single- and repeat-dose safety studies and in an ifetroban and aspirin interaction study in healthy volunteers. In the single-dose study, bleeding time was prolonged (2x baseline) in subjects receiving doses of ifetroban greater than 10 mg. Platelet aggregation induced by the TP receptor agonist U46619 was inhibited by all doses of ifetroban including 10 mg. This effect lasted for up to six days for the highest dose (1000 mg). Ifetroban also blocked arachidonic acid-induced platelet aggregation and partially inhibited collagen-induced aggregation. While epinephrine-induced primary aggregation was not affected by ifetroban, the secondary aggregation (degranulation) appeared to be inhibited. There was no drug effect on ADP-induced aggregation. Ifetroban alone or in combination with aspirin inhibited U46619-induced platelet aggregation. Treatment with aspirin alone did not prevent U46619-induced aggregation. Bleeding time was prolonged after all doses following the single dose and at steady state, although no dose-dependent increase in bleeding time was observed. No indication of accumulation effect was seen after nine days of dosing. No significant effect on urinary excretion of TXA₂ and prostacyclin metabolites was observed. In the aspirin interaction study, urinary excretion of both 2,3-dinor-TXB₂ and 2,3-dinor-6-keto-PGF_{1α} was decreased after administration of 325 mg of aspirin alone and 325 mg of aspirin + 250 mg ifetroban. Administration of ifetroban alone had no effect on urinary excretion of either 2,3-dinor-TXB₂ or 2,3-dinor-6-keto-PGF_{1α}. Thus, TP receptor blockade has no effect on the synthesis of vasoprotective PGI₂. *Of specific importance to our proposed trial, no significant safety concerns emerged in the studies of ifetroban with aspirin.*

Ifetroban was the subject of 24 controlled and uncontrolled human pharmacology and pharmacokinetic studies. It was also the subject of eight placebo-controlled clinical trials for various cardiovascular indications which are summarized in **Table 2**. The incidence rate of adverse events was generally comparable between the ifetroban-treated subjects and the placebo-treated subjects. Bradycardia was reported more often in the ifetroban group (N=32; 3.3%) than with placebo (N=7; 1.2%). Gastrointestinal events tended to occur more often in the ifetroban subjects than in the placebo subjects, although incidence rates were too small to suggest a trend or pattern. The most frequently reported adverse events (N; % ifetroban vs. N; % placebo) were headache (N=80; 8.4 vs. N=47; 7.7), musculoskeletal pain (N=48; 5.0 vs. N=19; 3.1), angina pectoris (N=33; 3.5 vs. N=22; 3.6), bradycardia (N=32; 3.3 vs. N=7; 1.2), myocardial infarction (N=28; 2.9 vs. N=18; 3.0), nausea/vomiting (N=25; 2.6 vs. N=10; 1.6), dyspepsia (N=24; 2.5 vs. N=9; 1.5), upper respiratory infection (N=24; 2.5 vs. N=9; 1.5), hematoma (N=23; 2.4 vs. N=8; 1.3), coronary artery bypass (N=22; 2.3 vs. N=10; 1.6), coronary angioplasty (N=21; 2.2 vs. N=10; 1.6), abdominal pain (N=20; 2.1 vs. N=10; 1.6), and anxiety/nervousness (N=19; 2.0 vs. N=9; 1.5). All remaining events occurred at a rate less than 2.0% in both treatment groups except for dizziness which occurred in 2.1% (N=13) of placebo-treated subjects (ifetroban: N=13; 1.9%).

Table 2. Number of subjects exposed to ifetroban in clinical studies.

		Subject Exposure	
		Ifetroban	Placebo
Clinical Pharmacology/Pharmacokinetics			
	Human Pharmacology	189	49
	Pharmacokinetic	154	0
Clinical Trials			
	Silent Ischemia (CV124-008)	58	55
	Stable angina (CV124-009)	105	52
	Unstable angina (CV124-011)	315	166
	PTCA (CV124-012)	90	35
	PVD (CV124-014)	137	44
	Post MI (CV124-015)	149	149
	Forearm blood flow in HF (CV124-018)	20	23
	Venous ulcers (CV139-001)	82	83
	Total Subjects	1299	656

5.1.1. Reproductive Risks and Toxicology for Ifetroban

Reproductive Risks:

Pregnant and nursing females will not be included in clinical trials of ifetroban. Furthermore, sexually active enrollees should be counselled against either becoming pregnant or fathering a child while participating in ifetroban clinical trials. Acceptable methods of male birth control include abstinence, 3-months post vasectomy, or condom use in combination with spermicide. Females of nonchildbearing potential may be allowed to participate provided that they are either 12-months post-menopausal prior to the first dose of study drug or have been surgically sterilized (e.g. tubal ligation or hysterectomy). Females of childbearing potential may be allowed to participate provided they use an acceptable method of contraception. Acceptable female methods of birth control include abstinence, condom used in combination with spermicide, oral contraceptives or contraceptive patch, contraceptive ring, or an implanted intrauterine device. Ifetroban appears to be teratogenic in rodents. Embryo-fetal toxicity was observed at doses of 100 and 1000 mg/kg administered orally by gavage once daily during gestation and maternotoxicity was seen at the 1000 mg/kg dose. No drug-related changes in the dams or fetuses were seen at the 10 mg/kg level. While these levels are well in excess of those studied in clinical trials thus far, the effects of ifetroban on human fetal development are unknown.

Rat Model

An initial teratology study in rats examined once daily doses (750 and 1500 mg/kg) of ifetroban administered by oral gavage to presumed pregnant rats on days 6 through 15 of gestation. There was a high incidence of resorptions at the doses studied (Lochry 1993, Internal Report 93012).

A reproductive toxicity study conducted in rats investigated once daily doses of ifetroban administered by oral gavage (7, 70, and 700 mg/kg) to both male and female rats prior to mating (4 week in males and 2 week in females) and during gestation. No reproductive effects in terms of fertility or early embryonic development were detected (Lochry 1995, Internal Report 94020).

In a second reproductive toxicity study, rats were given once daily doses (7.5, 75, 750 mg/kg) of ifetroban by oral gavage (gestation days 6-21) were well tolerated at doses up to 75 mg/kg. At 750 mg/kg, ifetroban was deemed toxic resulting in mortality, body weight loss, and enlarged adrenals and kidneys in the dams and an increased frequency of stillbirths and poor pup survival in the offspring (Gietl 1996, Internal Report 95201).

In a study of embryo-fetal development in rats, ifetroban was administered orally by gavage to presumed-pregnant rats once daily on days 6 through 15 of gestation at doses of 10, 100, or 1000 mg/kg. There were no drug-related changes in the dams or fetuses at 10 mg/kg. At 100 mg/kg, maternal liver weights were increased and the offspring demonstrated dilated lateral ventricles in the brain. At 1000 mg/kg, the dams again demonstrated increased liver weights as well as mortality associated with stomach lesions (concretions, ulcers, perforations, thickened mucosa, and/or multifocal discoloration of the stomach); body-weight loss; decreased food consumption; increased incidences of chromodacryorrhea, piloerection, and salivation or regurgitation of the dosing solutions; and increased kidney and spleen weights. Embryo-fetal toxicity at 1000 mg/kg included increased resorptions with an associated decrease in live-litter size, enlarged subarachnoid space of the brain, irregular ossification of the sternum, and decreased fetal weights with related developmental delays in ossification of the vertebrae, sternebrae, metacarpals, metatarsals, and phalanges. Ifetroban is therefore considered teratogenic in rats (Internal Report 94211, Feb 1996).

Rabbit Model

A reproductive toxicity study conducted in rabbits investigated once daily doses of ifetroban administered by oral gavage (4, 40, and 400 mg/kg) to presumed pregnant females on days 6 through 18 of gestation. No changes were seen in animals receiving either 4 or 40 mg/kg. At 400 mg/kg, maternal findings included body weight loss and decreased food consumption and the offspring demonstrated sternal defects (Jahn 1995, Internal Report 94207).

5.2. Risks of Investigational Product or Intervention cited in Medical Literature

5.3. Risks of Other Protocol Specified Medications

Risks of montelukast. Montelukast is a widely prescribed, once daily oral therapy approved for the treatment of asthma and allergic rhinitis. It is commonly prescribed as a treatment for AERD because of the established prominent role for the cysLTs in the disease. It is useful for reducing the severity of bronchoconstrictor responses to aspirin administration, likely due to its ability to competitively antagonize the effects of LTC₄ and LTD₄ acting at CysLT₁R. Montelukast is generally safe and well tolerated. The most common adverse reactions to montelukast identified in placebo-controlled trials (incidence \geq 5% and greater than placebo; listed in descending order of frequency) were upper respiratory infection, fever, headache, pharyngitis, cough, abdominal pain, diarrhea, otitis media, influenza, rhinorrhea, sinusitis,

and otitis. Additional reactions reported voluntarily during post-approval use of montelukast are of unknown frequency, and causality is not established. These include increased bleeding tendency, hypersensitivity reactions including anaphylaxis, hepatic eosinophilic infiltration, agitation including aggressive behavior or hostility, anxiousness, depression, dream abnormalities, hallucinations, insomnia, irritability, restlessness, somnambulism, suicidal thinking and behavior (including suicide), tremor, drowsiness, paresthesia/hypoesthesia, seizures, palpitations, epistaxis, diarrhea, dyspepsia, nausea, pancreatitis, vomiting, and hepatitis. Cases of eosinophilic granulomatosis with polyangiitis (Churg-Strauss syndrome) have been reported as well. Most, but not all, of these cases have been associated with the reduction of oral glucocorticoid therapy.

Risks of aspirin treatment. Aspirin, or acetylsalicylic acid, is a nonsteroidal anti-inflammatory drug primarily used to temporarily relieve fever and minor aches and pains due to: headache, colds, muscle pain, toothache, menstrual pain, and arthritis pain. In this study we will be using the generic form of Bayer Aspirin Regimen (81 mg) and Ecotrin (325 mg). Aspirin is FDA approved and will be open label throughout the entire study. **Visit 2** of the intervention study involves desensitization to aspirin followed by twice daily administration of aspirin at 650 mg, which the patients will then continue as part of their standard medical regimen. Aspirin is being used as both a provocative agent and a therapeutic. The risks of aspirin treatment after desensitization are described here, whereas the risks of the aspirin desensitization procedure appear below. Treatment of individuals with AERD with aspirin is an accepted approach and a standard of practice for individuals with AERD whose sinonasal disease cannot be adequately controlled with topical or systemic glucocorticoid therapy. The most common side effects of aspirin are bruising, gastrointestinal bleeding, cerebral hemorrhage, gastric irritation, and tinnitus. In a study of aspirin at 650 mg twice daily as a long-term (1 year) treatment for AERD, 14% of 172 patients discontinued aspirin due to side effects, and 70% had a clinical benefit.¹¹

Risks of corticosteroids. Virtually all subjects will have been on inhaled corticosteroids prior to enrollment in the study, and some will have been maintained on chronic oral steroids. Corticosteroid dosing will not be changed for this study. Nonetheless, subjects will be informed that when taken at high doses for extended periods, inhaled corticosteroids can produce hoarseness, sore throat, and thrush, as well as cause adrenal gland suppression, weight gain, bruising of the skin, and diabetes. Inhaled corticosteroids have also been associated with reduced growth velocity in children, but subjects in our study will all be age 18 and over.

5.4. Risks of Study Procedures

Risks of aspirin desensitization procedure. All individuals with AERD will experience a clinical reaction to aspirin, most often at a dose of 81 mg or below. By using the modified Scripps Institute protocol,³² limiting the study to individuals with stable asthma and no history of life-threatening reaction to COX inhibitors, and administering montelukast to all individuals undergoing the challenge, the procedure can safely be done in an ambulatory setting and is routinely performed in the Allergy Clinic at the BWH. To ensure safety of the challenge, vital signs will be obtained every 90 minutes, and patients are instructed to report any of the following symptoms; cough, dyspnea, chest tightness, rhinorrhea, congestion, sneeze, ocular pruritis and discharge. Spirometry is repeated before each dose, or at the time symptoms are reported. A decrease in pre-challenge FEV₁ of 15% or more is considered indicative of a positive lower respiratory tract reaction. In our experience, ~60% of individuals with AERD who are treated with montelukast develop airflow obstruction of this magnitude, while the remainder experience a reaction confined to the sinonasal tract. In addition to respiratory symptoms, occasionally extrapulmonary symptoms occur as well, which can include gastrointestinal manifestations (abdominal discomfort, nausea, vomiting, or diarrhea) and skin manifestations (flushing, itching, and rash). Systemic reactions that involve the cardiovascular system are very rare in this selected population.

Injectable adrenalin, oxygen, and resuscitation equipment are present in the ARC in the unlikely event of a systemic reaction, as are physicians skilled in resuscitation.

Risks of ACQ, SNOT-22, and TNSS questionnaires. There are no risks associated with questionnaires.

Risk of blood draw. Risks associated with drawing blood include some pain when the needle is inserted. There is a small risk of bruising and/or infection at the place where the needle enters the arm. Some people may experience lightheadedness, nausea or fainting. It is possible to develop an infection, but this is rare and can be treated.

Risk of spirometry. Occasionally, individuals may develop a slight dizzy feeling and/or temporary cough and/or chest discomfort when performing breathing tests. These tests are used in hundreds of laboratories throughout the world on a daily basis without harmful effects.

Risks of Exhaled Nitric Oxide (FeNO). There are no known risks for exhaled nitric oxide collection.

Nasal fluid and cell collection. The nasal procedures that we will use to collect fluid and cells from the nose may be uncomfortable. When using a nasal sponge, the absorbent cotton material will increase in size with absorption of nasal discharge and may result in transient blockage of the nostrils or sensation of fullness or pressure. Local irritation of the nostril is possible which could include blood-tinged discharge that is expected to resolve on its own. To minimize the possibility of inducing blood-tinged discharge, we will alternate which nostril is used for nasal sample collection. Risk for infection will be minimized by using sterile absorbent material for each collection. Rinsing the nose with saline solution may result in accidental swallowing of the saline solution and brushing the inside of the nose may cause minor local bleeding.

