suspected AERD will be enrolled in this study with the anticipation that there will be a dropout rate of 10-20%. All subjects will have a clinical history consistent with AERD (asthma, nasal polyposis, and a history of a suspected reaction to a nonselective COX inhibitor). All subjects will be on standard therapy for persistent asthma, which may include some combination of inhaled glucocorticoids, oral glucocorticoids, long- and short-acting β -agonists, and CysLT₁R antagonists. We will exclude individuals being treated with omalizumab (monoclonal anti-IgE) or mepolizumab (monoclonal anti-IL-5), as the effects of these medications on the aspirin-induced reactions in AERD are not known. Detailed Inclusion and Exclusion criteria are listed in Section 4.2 and 4.3. We have found that all of the subjects who are currently enrolled in our trial of prasugrel and meet these strict inclusion criteria exhibited respiratory reactions to aspirin, confirming their diagnosis of AERD. The Study Schema overview is shown in **Figure 3**.

At a Screening Visit for patients with AERD, the study will be explained, and the participant will sign informed consent before undergoing any procedures. A physical exam, baseline ECG, spirometry and lab work (CBC, urine pregnancy) will be performed. Assessments of asthma control (ACQ score, which evaluates asthma control over the preceding 1 week), and nasal symptoms (SNOT-22 score, which assesses symptoms over the preceding 2 weeks) will also be obtained.

There will be a 2-week Run-In after the Screening Visit during which subjects will begin taking montelukast 10mg daily (if not already on montelukast as part of their regular asthma care) and will stop taking zileuton (if they are on

zileuton as part of their regular asthma care). A telephone encounter (**Phone Call 1**) 1 week later will ensure safety and confirm stable asthma.

After the 2-week Run-In Period on montelukast, subjects will come into the ARC for **Visit 1**. Interval history, physical exam, ACQ, SNOT-22, pre-challenge TNSS and spirometry will be recorded, along with FeNO. Blood will be drawn for CBC/differential, and cellular profiling and activation assays. A urine sample will be collected for pregnancy and eicosanoid metabolites. Nasal lavage for cytokine and eicosanoid measurements and a nasal epithelial scraping sample for RNA extraction will be taken. Subjects will be randomized to receive ifetroban (200 mg dose per day), or placebo for 4 weeks.

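### Section 5.4 relies on keeping out patients with a past life-threatening COX-inhibitor reaction, but none of the 21 criteria in 4.2 and 4.3 keeps them out

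*Combined protocol and SAP*

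**What the plan says.** Section 5.4 (Risks of Study Procedures) gives four reasons for judging the aspirin challenge acceptable outside hospital: a modified Scripps protocol, stable asthma, the absence of a past life-threatening reaction, and montelukast for everyone. The second and third are expressed together as "limiting the study to individuals with stable asthma and no history of life-threatening reaction to COX inhibitors". From the four it concludes that "the procedure can safely be done in an ambulatory setting". It adds that "Systemic reactions that involve the cardiovascular system are very rare in this selected population".

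Section 3.1 directs the reader elsewhere for the operative rules: "Detailed Inclusion and Exclusion criteria are listed in Section 4.2 and 4.3". Section 4.2 opens with "Individuals who meet all of the following criteria are eligible for enrollment as study participants" and has 7 numbered items. Section 4.3 has 14, and meeting any one of them makes a person ineligible.

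**The concern.** Section 5.4 presents the severity restriction as a fact about who is in the study. Site staff decide eligibility from 4.2 and 4.3, and those lists do not contain it. The two parts of the protocol therefore classify the same patient differently.

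The stake is safety. Section 5.4 expects every participant with AERD to react to aspirin, and about 60% of those on montelukast to lose at least 15% of FEV₁. Sections 3.1 and 8.3 also limit symptom relief to albuterol and ipratropium for 3 hours after onset, unless safety requires more. The severity of earlier reactions is a selection safeguard that the authors chose and relied on. The reassurance about cardiovascular reactions is given for a selected population, and one part of that selection is not secured by any criterion.

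**Working it through.** No power or alpha figure is involved. The check is a reading of the lists and a tracing of each safety measure to operative text.

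**Step 1: count the criteria.** Section 4.2 has 7 items and 4.3 has 14; 7 + 14 = 21. Items that name a life-threatening or otherwise severe reaction to a COX inhibitor: 0 of 7 and 0 of 14, so 0 of 21. Both lists are numbered without gaps, so nothing appears to have been lost in extraction. The synopsis inclusion and exclusion lists do not contain the limit either.

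**Step 2: trace the four measures in 5.4.**

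| Measure in 5.4 | Operative text |
|---|---|
| Graded challenge procedure | 8.3: 40.5, 81, 162 and 325 mg at 90-minute intervals |
| Stable asthma | 4.2 item 4 |
| No past life-threatening COX-inhibitor reaction | none found |
| Montelukast for all | 7.1.1 |

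Three of four are carried through. Two of the four restrict who may enter, and one of those two is listed. The first row treats the 8.3 schedule as the modified Scripps protocol, which 8.3 does not name. The finding does not depend on that match.

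**Step 3: test the nearest items.**

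- *4.2 item 3* requires "History of pathognomonic reactions to aspirin or other nonselective COX inhibitors". It asks for at least two such reactions with airway features, or a confirmatory physician challenge. It sets the type of reaction and places no ceiling on severity.
- *4.2 item 4* requires "no hospitalizations or ER visits for asthma for at least 6 months prior to Visit 1". It covers asthma events in a short window, so a life-threatening drug reaction years earlier passes.
- *4.3 item 2* is the only hypersensitivity exclusion, and it concerns montelukast.
- *4.3 item 12* covers other medical problems "which, in the opinion of the investigator, may pose additional risks from participation in the study". It permits exclusion case by case and does not require it.

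**Step 4: apply the lists to a case.** Take a patient with asthma, polyps and two qualifying reactions, one of which led to intubation years ago, who is now stable and otherwise meets every item. Unless an investigator invokes item 12, this patient is eligible under 4.2 and 4.3 and proceeds to the Visit 2 challenge. Under 5.4 the same patient is not in the study.

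**Step 5: is the omission likely to be deliberate?** The lists suggest not. The narrative exclusion of two biologics in 3.1 reappears as 4.3 item 8. Lifetime-history bars appear where they were wanted: bleeding diathesis (item 4), gastrointestinal bleeding (item 5) and rhythm disturbances (item 9).

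**The case against.** The strongest reply is that the limit is already in the protocol. Section 5.4 states it without qualification, the site investigator signs to follow the criteria written in the protocol as a whole, and 14.1 allows no departures. On that reading, enrolling such a patient is already forbidden and only a list entry is missing. This has some force, and it makes the problem an inconsistency between sections. It does not settle the matter: 14.1 does not say which section governs when two disagree, 4.2 and 4.3 state their own conditions for eligibility, and the process in 14.2 begins once a deviation has been found.

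A second reply is that this is one site run by specialists, drawing largely on their own patients. Inclusion 3 obliges them to establish the reaction history, and exclusion 12 lets them act on it with 5.4 in mind. That stands as real mitigation. It remains a judgement, whereas 5.4 describes a categorical limit. The eligibility procedures listed in 8.2 (examination, spirometry, laboratory tests, ACQ, SNOT-22, ECG) include nothing aimed at the severity of past reactions.

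Third, desensitization is standard care at this institution. Graded dosing, observation, injectable adrenalin, resuscitation equipment and the suspension rules in 11.5 all still apply. That also stands, and it limits the weight of the finding to one missing criterion.

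**Conclusion.** The concern holds. A restriction that 5.4 uses to support outpatient provocation appears in 0 of 21 eligibility criteria, and no other item has the same effect. As written, 4.2 and 4.3 can admit a patient whom 5.4 says is not in the study.

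The size is one missing criterion; the rest of the safety case is untouched. The documents do not say how many candidates have such a history, and no event rate is claimed here. The sample size, power and primary analysis do not change. The conclusion assumes that eligibility is decided from 4.2 and 4.3, as 3.1 indicates. It should be corrected because it bears on participant safety and the correction is small.

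**What to change.** Add a numbered exclusion to 4.3 for any past life-threatening reaction to aspirin or another COX inhibitor, and repeat it in the synopsis. Give it a working definition so that it can be applied consistently. A reaction that required intubation, ICU admission or vasopressor support is one example; the final wording is a clinical decision.

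If the investigators do intend to enrol such patients, correct 5.4 instead and justify the ambulatory setting for them specifically.

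The cost is one line in 4.3, its counterpart in the synopsis, and possibly a few fewer eligible subjects.
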